5.4 Stratification

'Window of opportunity' chemotherapy is not advised or administered to patients with NMIBC who undergo radical cystectomy. As such, although there will not be an active attempt to enrich the study population for such patients, it is likely that the study cohort will contain a significant group with NMIBC. However, trial accrual will be sequential and according to the earlier described eligibility criteria. As such, no active attempt at stratification will be made.

5.5 Concomitant Medications/Vaccinations

Medications or vaccinations specifically prohibited in the exclusion criteria are not allowed during the ongoing trial. If there is a clinical indication for one of these or other medications or vaccinations specifically prohibited during the trial, discontinuation from study therapy or vaccination may be required. The treating physician may choose to discuss any questions regarding this with the PI of the study; however, the final decision on any supportive therapy or vaccination rests with the subject's treating physician.

5.5.1 Acceptable Concomitant Medications

All treatments that the treating physician considers necessary for a subject's welfare may be administered at the discretion of the treating investigator in keeping with the community standards of medical care. All concomitant medications will be recorded in the medical record throughout the duration of the study, including prescription, over-the-counter (OTC), herbal supplements, and IV medications. Medications and fluids used for anesthesia and standard of care pre and post-op care will not be recorded for protocol purposes. Blood products, if administered, will be recorded.

Concomitant medications received within 28 days before the first dose of pembrolizumab and 30 days after surgery will be recorded. Concomitant medications administered beyond 30 days after surgery will be recorded only for serious adverse events (SAEs) and events of clinical importance (ECIs).

5.5.2 Prohibited Concomitant Medications

Subjects are prohibited from receiving the following therapies during the screening and treatment phase of this trial:

- Antineoplastic systemic chemotherapy or biological therapy
- Immunotherapy not specified in this protocol
- Live vaccines within 30 days prior to the first dose of study treatment and during the treatment phase of the study. Examples of live vaccines include, but are not limited to, the following: measles, mumps, rubella, varicella/zoster, yellow fever, rabies, BCG, typhoid vaccine and intranasal influenza vaccine.
- Systemic glucocorticoids for any purpose other than to modulate symptoms from an event of clinical interest of suspected immunologic etiology. The use of physiologic doses of corticosteroids may be approved after consultation with the principal investigator.

Subjects who, in the assessment by the investigator, require the use of any of the aforementioned treatments for clinical management should be removed from the trial. At that time, subjects may receive other treatment that the investigator deems to be medically necessary.

5.6 Rescue Medications and Supportive Care

5.6.1 Rescue Medications & Supportive Care

Participants should receive appropriate supportive care measures as deemed necessary by the treating investigator. Suggested supportive care measures for the management of AEs with potential immunologic etiology are outlined along with the dose modification guidelines in Section 5.2.2, [Table 3]. Where appropriate, these guidelines include the use of oral or IV treatment with corticosteroids, as well as additional anti-inflammatory agents if symptoms do not improve with administration of corticosteroids. Note that several courses of steroid tapering may be necessary as symptoms may worsen when the steroid dose is decreased. For each disorder, attempts should be made to rule out other causes such as metastatic disease or bacterial or viral infection, which might require additional supportive care. The treatment guidelines are intended to be applied when the Investigator determines the events to be related to pembrolizumab.

Note: If after the evaluation of the event, it is determined not to be related to pembrolizumab, the Investigator does not need to follow the treatment guidance. Refer to [Table 3] in Section 5.2.2 for guidelines regarding dose modification and supportive care.

It may be necessary to perform conditional procedures such as bronchoscopy, endoscopy, or skin photography as part of evaluation of the event.

5.7 Diet, Activity and Other Considerations

5.7.1 Diet

Subjects should maintain a normal diet unless modifications are required to manage an AE such as diarrhea, nausea or vomiting.

5.7.2 Contraception

Pembrolizumab may have adverse effects on a fetus in utero. Furthermore, it is not known if pembrolizumab has transient adverse effects on the composition of sperm.

For this trial, male subjects will be considered to be of non-reproductive potential if they have azoospermia (whether due to having had a vasectomy or due to an underlying medical condition).

Female subjects will be considered of non-reproductive potential if they are either:

(1) postmenopausal (defined as at least 12 months with no menses without an alternative medical cause; in women < 45 years of age a high follicle stimulating hormone (FSH) level in the postmenopausal range may be used to confirm a post-menopausal state in women not using hormonal contraception or hormonal replacement therapy. In the absence of 12 months of amenorrhea, a single FSH measurement is insufficient.);

OR

(2) have had a hysterectomy and/or bilateral oophorectomy, bilateral salpingectomy or bilateral tubal ligation/occlusion, at least 6 weeks prior to screening;

OR

(3) has a congenital or acquired condition that prevents childbearing.

Female and male subjects of reproductive potential must agree to avoid becoming pregnant or impregnating a partner, respectively, while receiving study drug and for 120 days after the last dose of study drug by complying with one of the following:

(1) practice abstinence† from heterosexual activity;

OR

(2) use (or have their partner use) acceptable contraception during heterosexual activity.

Acceptable methods of contraception are‡:

Single method (one of the following is acceptable):

- intrauterine device (IUD)
- vasectomy of a female subject's male partner
- contraceptive rod implanted into the skin
- diaphragm with spermicide (cannot be used in conjunction with cervical cap/spermicide)
- contraceptive sponge (nulliparous women only)
- male condom or female condom (cannot be used together)
- hormonal contraceptive: oral contraceptive pill (estrogen/progestin pill or progestin-only pill), contraceptive skin patch, vaginal contraceptive ring, or subcutaneous contraceptive injection

[†]Abstinence (relative to heterosexual activity) can be used as the sole method of contraception if it is consistently employed as the subject's preferred and usual lifestyle and if considered acceptable by local regulatory agencies and ERCs/IRBs. Periodic abstinence (e.g., calendar, ovulation, sympto-thermal, post-ovulation methods, etc.) and withdrawal are not acceptable methods of contraception.

[#]If a contraceptive method listed above is restricted by local regulations/guidelines, then it does not qualify as an acceptable method of contraception for subjects participating at sites in this country/region.

Subjects should be informed that taking the study medication may involve unknown risks to the fetus (unborn baby) if pregnancy were to occur during the study. In order to participate in the study subjects of childbearing potential must adhere to the contraception requirement (described above) from the day of study medication initiation (or 30 days prior to the initiation of study medication for oral contraception) throughout the study period up to 120 days after the last dose of trial therapy. If there is any question that a subject of childbearing potential will not reliably comply with the requirements for contraception, that subject should not be entered into the study.

5.7.3 Use in Pregnancy

If a subject inadvertently becomes pregnant while on treatment with pembrolizumab, the subject will immediately be removed from the study. Additionally, the study investigator will make every effort to obtain permission to follow the outcome of the pregnancy and report the condition of the fetus or newborn. The site will contact the subject at least monthly and document the subject's status until the pregnancy has been completed or terminated. The outcome of the pregnancy will be reported to the Institutional Review Board (IRB), IND Office, and to Merck without delay if the outcome is a serious adverse experience (e.g., death, abortion, congenital anomaly, or other disabling or life-threatening complication to the mother or newborn). The IND Office will be notified through the eSAE system.

The study investigator will make every effort to obtain permission to follow the outcome of the pregnancy and report the condition of the fetus or newborn to the Sponsor. If a male subject impregnates his female partner the study personnel at the site must be informed immediately and the pregnancy reported to the Institutional Review Board (IRB), IND Office, and to Merck without delay.

5.7.4 Use in Nursing Women

It is unknown whether pembrolizumab is excreted in human milk. Since many drugs are excreted in human milk, and because of the potential for serious adverse reactions in the nursing infant, subjects who are breast-feeding are not eligible for enrollment.

5.8 Subject Withdrawal/Discontinuation Criteria

Subjects may withdraw consent at any time for any reason or be dropped from the trial at the discretion of the investigator or treating physician should any untoward effect occur. In addition, a subject may be withdrawn by the principal investigator if enrollment into the trial is inappropriate, the trial plan is violated, or for administrative and/or other safety reasons.

A subject must be discontinued from the trial for any of the following reasons:

- The subject or legal representative (such as a parent or legal guardian) withdraws consent
- Unacceptable adverse experiences as described in Table 3 and section 5.6.1
- Unexpected intercurrent illness that prevents further administration of study treatment
- Investigator's decision to withdraw the subject
- The subject has a confirmed positive serum pregnancy test
- Noncompliance with study treatment or procedure requirements
- The subject is lost to follow-up: two failed attempts to contact the patient by phone or e-mail AND one unanswered certified letter sent to subject's registered home address.
- Completed study participation or of follow up from initiation of study treatment.

Subjects who prematurely discontinue from the study treatment, will return to clinic within 30 days of treatment discontinuation to complete the safety assessments listed under the

“Early Treatment Discontinuation” visit listed in Section 6. All other subjects will continue on the follow-up phase through 90 days post-op.

6.0 STUDY FLOW CHART

STUDY PHASE	SCREENING PHASE	TREATMENT PHASE				FOLLOW-UP PHASE	EARLY TREATMENT DISCONTINUATION
VISIT/CYCLE	SCREENING	CYCLE #1 (Week 1)	CYCLE #2 (Week 4)	PRE-OP/SAFETY VISIT (Week 7)	SURGERY (Week 6- 8)	FOLLOW-UP	
Scheduling window (days)	-28 to -1	1(± 3)	21(± 3)	35-49(± 3)	42-56(± 3)	30 day (± 7) and 90 day (± 7) Post Op	
Informed Consent	X						
Inclusion/Exclusion Criteria	X						
Demographics/Medical history	X						
Concomitant Medications	X	X	X	X	X	X ⁸	X ⁸
Pembrolizumab Administration		X	X				
Assessment of Disease Extent ¹	X						
Review of Adverse Events	X	X	X	X	X	X	X
Full Physical Exam	X						X
Directed Physical Exam		X	X	X		X	
Vital Signs and Weight	X	X ²	X ²	X		X	X
ECOG Performance Status	X	X	X	X		X	X
Pregnancy Test	X	X ³					
PT/INR and aPTT	X ⁹	X	X	X		X	X
CBC with Diff	X ⁹	X	X	X		X	X

Proprietary Information of MD Anderson

2017-0057

January 9, 2019

Page 28

Comprehensive Metabolic Panel ⁴	X ⁹	X	X	X		X	X
Urinalysis ⁵	X ⁹	X	X	X		X	X
T3, FT4 and TSH	X ⁹	X	X	X		X	X
Pulmonary Function Tests	X						
ACTH, Cortisol	X	X	X				
ESR, CRP	X	X	X				
Testosterone, FSH, LH (males)	X	X	X				
Estrogen, FSH, LH (females)	X	X	X				
Archival Tissue Collection ⁶	X				X		
Feces and Urine for microbiome studies	X			X		X ¹⁰	
Blood for Correlative Studies ⁷	X		X	X		X	
Cystectomy					X		

¹ A complete assessment of disease extent will be made at screening per SOC guidelines, and will include but not be limited to diagnostic endoscopy with biopsy/resection of the index lesion for pathologic diagnosis. Additionally an examination and assessment for palpable disease will be made. Cross sectional imaging of the chest, abdomen and pelvis with the addition of whole body nuclear medicine bone imaging where clinically indicated will complete the staging evaluation. Exams performed within 6 weeks prior to screening will be accepted for inclusion in the study if deemed appropriate by the treating physician

² Pre and post pembrolizumab dose during treatment administration days

³ Female subjects of childbearing potential should have a negative urine or serum pregnancy test within 72 hours prior to receiving the first dose of study medication. If the urine test is positive or cannot be confirmed as negative, a serum pregnancy test will be required.

⁴ Includes: Albumin, alkaline phosphatase, ALT, AST, LDH, electrolytes, uric acid, calcium, glucose, phosphorus, magnesium, total bilirubin, total protein, BUN and creatinine

⁵ Microscopic exam if abnormal results are noted

⁶ Archival tissue from a newly obtained core or excisional biopsy of a tumor lesion. Newly-obtained is defined as a specimen obtained up to 6 weeks (42 days) prior to initiation of treatment on week 1. Subjects for whom newly-obtained samples cannot be provided (e.g. inaccessible or subject safety concern) may collect tissue from a previously archived specimen. Additionally, archival tissue from the surgical specimen at the time of cystectomy will also be collected

⁷ Up to 60 mL of blood at baseline or pre-treatment, after the first cycle of treatment, after the second cycle of treatment and post-cystectomy will be collected and banked for future research

⁸ Concomitant medications administered beyond 30 days after surgery will be recorded only for serious adverse events (SAEs) and events of clinical importance (ECIs).

⁹ Within 14 days prior to first dose of pembrolizumab

¹⁰ 90 day post op only

7.1 STUDY PROCEDURES

The Study Flow Chart - Section 6.0 summarizes the trial procedures to be performed at each visit. Individual trial procedures are described in detail below. It may be necessary to perform these procedures at unscheduled time points if deemed clinically necessary by the investigator.

Furthermore, additional evaluations/testing may be deemed necessary by the investigator for reasons related to subject safety. In some cases, such evaluation/testing may be potentially sensitive in nature (e.g., HIV, Hepatitis C, etc.), and thus local regulations may require that additional informed consent be obtained from the subject. In these cases, such evaluations/testing will be performed in accordance with those regulations.

7.2 Informed Consent

The Investigator or qualified designee must obtain documented consent from each potential subject prior to participating in this clinical trial. The informed consent process will adhere to MDACC's Institutional guidelines and applicable laws and regulations.

7.3 Inclusion/Exclusion Criteria

All inclusion and exclusion criteria will be reviewed by the investigator or qualified designee to ensure that the subject qualifies for the trial.

7.4 Medical History

A medical history will be obtained by the investigator or qualified designee. Medical history will include all active conditions, and any condition diagnosed within the prior 10 years that are considered to be clinically significant. Details regarding bladder cancer status and a review of all prior cancer treatments including systemic therapies, radiation and/or surgeries will be included. Additionally, emphasis on autoimmune disorders and treatments for these conditions will be made.

7.5 Concomitant Medications Review

The investigator or qualified designee will review and record all medications taken by the subject within 28 days before the first dose of pembrolizumab and 30 days after surgery. Medications and fluids used for anesthesia and standard of care pre and post-op care will not be recorded. Blood products, if administered, will be recorded. Concomitant medications administered beyond 30 days after surgery will be recorded only for serious adverse events (SAEs) and events of clinical importance (ECIs).

7.6 Adverse Event (AE) Monitoring

The investigator or qualified designee will assess each subject to evaluate for potential new or worsening adverse events throughout the duration of the study. Adverse events will be graded according to NCI CTCAE Version 4.0. Toxicities will be characterized in terms regarding seriousness, causality, toxicity grading, and action taken with regard to study treatment. Refer to Section 8 for further details regarding assessing and recording adverse events.

Any related adverse events Grade >1 which are present at the time of discontinuation/withdrawal should be followed until the resolution of the AE to Grade 0-1.

7.7 Full Physical Exam

The investigator or qualified designee will perform a complete physical exam during the screening phase and early treatment discontinuation visit. Clinically significant abnormal findings during screening should be recorded as medical history.

7.8 Directed Physical Exam

The investigator or qualified designee will perform a directed physical exam as clinically indicated during the treatment and follow-up phases. Clinically significant abnormal changes from screening will be recorded as adverse events.

7.9 Vital Signs

Vital signs will be measured by triage clinic personnel as per standard of care during the study. Additionally, vital signs will be measured pre and post-treatment on weeks 1 and 4. Vital signs should include temperature, pulse, respiratory rate, weight and blood pressure. Height will be measured at screening only.

7.10 Eastern Cooperative Oncology Group (ECOG) Performance Scale

The investigator or qualified designee will assess ECOG performance status at every protocol visit as specified in the Study Flow Chart.

7.11 Tumor Imaging and Assessment of Disease

A complete assessment of disease extent will be made at screening following standard of care guidelines, and will include diagnostic endoscopy with biopsy/resection of the index lesion for pathologic diagnosis. Additionally an examination and assessment for palpable disease will be made. Cross sectional imaging of the chest, abdomen and pelvis with the addition of whole body nuclear medicine bone imaging where clinically indicated will complete the staging evaluation. Standard of care procedures/images performed within 6 weeks prior to

screening will be accepted for inclusion in the study if deemed appropriate by the treating physician.

7.12 Tumor Tissue Collection and Correlative Studies Blood Sampling

All participants will be required to participate in the collection of blood and tissue specimens for banking and future research studies.

7.13 Laboratory Assessments

Details regarding specific laboratory assessments are specified in Table 6. Laboratory tests for screening should be performed within 14 days prior to the first dose of pembrolizumab. Laboratory assessments for each subsequent visit can be conducted up to 72 hours prior to dosing/clinic visit. Results must be reviewed by the investigator or qualified designee and found to be acceptable prior to each dose of pembrolizumab.

7.14 Withdrawal/Discontinuation

Subjects who prematurely discontinue from the study treatment, will return to clinic within 30 days of treatment discontinuation to complete the safety assessments listed under the “Early Treatment Discontinuation” visit listed in Section 6. All other subjects will continue on to the follow-up phase (30 and 90 day visits after surgery).

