5.2.1 Dose Selection

The rationale for selection of doses to be used in this trial is provided in Section 4.2.2.

Details on preparation and administration of pembrolizumab are provided in the Pharmacy Manual.

5.2.2 Dose Modification and toxicity management for immune-related AEs associated with pembrolizumab

AEs associated with pembrolizumab exposure may represent an immunologic etiology. These immune-related AEs (irAEs) may occur shortly after the first dose or several months after the last dose of pembrolizumab treatment and may affect more than one body system simultaneously. Therefore, early recognition and initiation of treatment is critical to reduce complications. Based on existing clinical study data, most irAEs were reversible and could be managed with interruptions of pembrolizumab, administration of corticosteroids and/or other supportive care. For suspected irAEs, ensure adequate evaluation to confirm etiology or exclude other causes. Additional procedures or tests such as bronchoscopy, endoscopy, skin biopsy may be included as part of the evaluation. Based on the severity of irAEs, withhold or permanently discontinue pembrolizumab and administer corticosteroids. Dose modification and toxicity management guidelines for irAEs associated with pembrolizumab are provided in Table 3.

Table 3: Dose modification and toxicity management guidelines for immune-related AEs associated with pembrolizumab

General instructions:

1. Corticosteroid taper should be initiated upon AE improving to Grade 1 or less and continue to taper over at least 4 weeks.
2. For situations where pembrolizumab has been withheld, pembrolizumab can be resumed after AE has been reduced to Grade 1 or 0 and corticosteroid has been tapered. Pembrolizumab should be permanently discontinued if AE does not resolve within 12 weeks of last dose or corticosteroids cannot be reduced to ≤ 10 mg prednisone or equivalent per day within 12 weeks.
3. For severe and life-threatening irAEs, IV corticosteroid should be initiated first followed by oral steroid. Other immunosuppressive treatment should be initiated if irAEs cannot be controlled by corticosteroids.

Immune-related AEs	Toxicity grade or conditions (CTCAEv4.0)	Action taken to pembrolizumab	irAE management with corticosteroid and/or other therapies	Monitor and follow-up

Proprietary Information of MD Anderson

2017-0057

January 9, 2019

Page 17

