Grades 3 or 4 Grade 3: Prolonged (i.e., not rapidly responsive to symptomatic medication and/or brief interruption of infusion); recurrence of symptoms following initial improvement; hospitalization indicated for other clinical sequelae (e.g., renal impairment, pulmonary infiltrates) Grade 4: Life-threatening; pressor or ventilatory support indicated	
Stop Infusion.
 
Additional appropriate medical therapy may include but is not limited to:
 
Epinephrine** IV fluids Antihistamines NSAIDs Acetaminophen Narcotics Oxygen Pressors Corticosteroids
 
Increase monitoring of vital signs as medically indicated until the participant is deemed medically stable in the opinion of the investigator.
 
Hospitalization may be indicated.
 
**In cases of anaphylaxis, epinephrine should be used immediately.
 
Participant is permanently discontinued from further study drug treatment.
	No subsequent dosing

Appropriate resuscitation equipment should be available at the bedside and a physician readily available during the period of drug administration.
 
For further information, please refer to the Common Terminology Criteria for Adverse Events v4.0 (CTCAE) at http://ctep.cancer.gov
		

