9.2 Endpoints

9.1.1 Toxicity for Safety Monitoring (TOX)

TOX will be monitored for an approximate 3-month treatment time interval (2 cycles/6 weeks + surgery/2 week scheduling cushion + 30 day surgical complication evaluation). A patient will be considered to have a toxicity of concern (TOX) if any of the following apply:

- Any 30-day grade 3 or higher surgical complication at least possibly related to the treatment
- Any toxicity at least possibly related to the treatment that prevents surgery
 - Note, missing surgery due to progression or withdrawal will not count as a TOX event. Rapid progression is not seen with pembrolizumab.
- Death between the start of study and the 30-day post-surgical assessment will count as long as it is toxic death at least possibly related to the pembrolizumab or surgery. Deaths clearly unrelated to treatment will not count as an event.

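### Patients who stop pembrolizumab early but still have cystectomy have no scheduled post-operative visit under 5.8 and 7.14, although TOX runs to 30 days after surgery; 9.4 does not say how an unknown 30-day status is counted

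*Combined protocol and SAP*

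**What the plan says.** **Visits.** Sections 5.8 and 7.14 use the same rule for early stopping: "Subjects who prematurely discontinue from the study treatment, will return to clinic within 30 days of treatment discontinuation". Section 5.8 then adds: "All other subjects will continue on the follow-up phase through 90 days post-op". Section 7.14 closes the same way and names the 30- and 90-day visits. The flow chart in section 6.0 gives early treatment discontinuation its own column, separate from follow-up.

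**Who stops early.** Section 5.2.2 instructs: "Based on the severity of irAEs, withhold or permanently discontinue pembrolizumab and administer corticosteroids". Table 3 requires permanent discontinuation for several toxicities. For grade 3 or 4 infusion reactions Table 4 says: "Participant is permanently discontinued from further study drug treatment". Section 5.8 goes further. Under the lead-in "A subject must be discontinued from the trial for any of the following reasons" it lists "Unacceptable adverse experiences as described in Table 3 and section 5.6.1".

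**Endpoint.** One TOX criterion in 9.1.1 is "Any 30-day grade 3 or higher surgical complication at least possibly related to the treatment". Another is toxic death up to the 30-day post-surgical assessment.

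**Counting.** In 9.3, a treated patient is evaluable in monthly monitoring after 4 weeks without TOX, and a later TOX is added at the next monthly evaluation. A hold lasts until treated patients reach 30 days after surgery or have left the study. The sixth patient may enter only when at least 4 of the first 5 have completed 30 days after surgery without TOX. Section 9.4 reports TOX with a beta(1,1) credible interval and does not address unknown status.

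**The concern.** The instruction for early stoppers does not fit the endpoint. TOX needs to be known at post-operative day 30, but the only visit scheduled for these patients is timed from the day the drug stopped. Nothing says that they forgo cystectomy, which was already planned when they enrolled. Many will have stopped because of drug toxicity, so they are not a random subset, and peri-operative safety after pembrolizumab is the main question of the trial.

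Listing unacceptable toxicity as a reason to leave the trial, and not only the drug, adds doubt about whether such a patient counts as off study for the hold in 9.3. If a post-operative TOX went unrecorded, monthly monitoring would keep the patient as TOX-free and the reported rate would be too low.

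Toxicity that prevents surgery is outside this point. It is a TOX in its own right, needs no post-operative visit, and has a separate stopping rule in 5.3.

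**Working it through.** **1. The plan's own figures.** For 3 TOX in 20 with a beta(1,1) prior, the posterior is Beta(4,18). Its 2.5% and 97.5% quantiles are 5.4% and 36.3%, as stated in 9.2. The stopping table in 9.3 also reproduces from P(p > 0.15 | data) > 0.95: 2/5 gives 0.953, 3/9 gives 0.950, 4/13 gives 0.953, 5/17 gives 0.958 and 6/20 gives 0.971.

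**2. Timing of the discontinuation visit.** Let D be the day treatment stops and S the day of surgery. The visit is due by D + 30 and TOX closes at S + 30. The visit is therefore due (S + 30) − (D + 30) = S − D days too early.

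Inputs from the flow chart: surgery on day 42 to 56 (± 3), so S is 39 to 59 and post-operative day 30 is day 69 to 89. Dose 2 is on day 21 (± 3), so its latest date is day 24.

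| Stop | Visit due by | Days before post-operative day 30 |
|---|---|---|
| Dose 1, D = 1 | day 31 | 69 − 31 = 38 to 89 − 31 = 58 |
| Latest dose 2 date, D = 24 | day 54 | 69 − 54 = 15 to 89 − 54 = 35 |

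For a stop at dose 1, the visit is due 39 − 31 = 8 to 59 − 31 = 28 days before the operation itself. A withheld dose 2 that is never given has no stated stop date, so no gap is computed for it.

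**3. What the serious-event window covers.** Sections 8.1 and 8.3.1 capture serious events to D + 90. This reaches post-operative day 30 when D + 90 ≥ S + 30, that is, when S − D ≤ 60. For D = 1 the window runs to day 91, against a latest post-operative day 30 of day 89, so it covers the TOX period when surgery is in the flow-chart window. If surgery comes more than 60 days after the last dose, the window closes too soon. Serious events related to treatment must still be reported after it (8.3.1).

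**4. What one missed event can do.** With 3/9 the posterior probability is 0.950 and the rule stops. With 2/9 it is 0.820 and the trial continues. At 3/10 it is about 0.93, which does not stop, so losing one event there would change nothing.

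**5. What a two-way report would show (illustration only).** Start from 3 known TOX in 20:

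| Patients with unknown status | Counted as no TOX | Counted as TOX |
|---|---|---|
| 1 | 15% (5.4 to 36.3) | 4/20 = 20% (8.2 to 41.9) |
| 2 | 15% (5.4 to 36.3) | 5/20 = 25% (11.3 to 47.2) |

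The documents give no figure for how many patients would be in this position.

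**The case against.** The case against is substantial, and most of it stands.

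- **Serious events.** They are captured for 90 days after treatment stops, whatever their cause. Toxic death is always serious. Table 5 defines grade 3 partly by hospitalization or its prolongation, so many grade 3 or higher surgical complications would be reported as serious.
- **Other duties.** Section 8.1 asks for all adverse events to 30 days after surgery, with no exception for early stoppers. Section 7.6 follows related events above grade 1 that are present at discontinuation. The safety reports in 9.3 update earlier patients at each submission.
- **General visit text.** Section 2.2 describes the post-operative visits for patients in general, and 5.3 does so for the first three patients, without exceptions. The wording in 5.8 and 7.14 may simply be loose.
- **Denominator.** Section 2.1.7 already evaluates safety in all treated patients.
- **Sixth patient.** The condition in 9.3 requires completed follow-up, so an unknown status does not pass as TOX-free there.
- **Scope.** Only two doses are planned. Toxicity arising after dose 2 is complete does not trigger the early-stop rule.

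What remains is that these are reporting duties and general descriptions. None schedules a post-operative assessment for an early stopper, and the more specific text in 7.14 points the other way.

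A reader might infer that post-operative toxicity in these patients is not collected at all, that every permanent discontinuation in Table 3 is affected, or that the TOX rate is biased by an amount that can be calculated. The documents do not support these readings. The duties above contradict the first, the two-dose schedule contradicts the second, and no figure is given from which to estimate the third.

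**Conclusion.** The point holds in a limited form. For patients stopped after dose 1, or during the dose 2 infusion, who still have cystectomy, 5.8 and 7.14 conflict with the TOX window, with the adverse-event duty in 8.1 and with the visit text in 2.2 and 5.3. The loss is of a scheduled assessment. It weakens capture mainly of grade 3 or higher surgical complications that are not reported as serious. Separately, monthly monitoring treats such a patient as TOX-free unless a later TOX is reported, and 9.4 leaves unknown 30-day status undefined.

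The timing result assumes surgery within the flow-chart window. The reassurance from the 90-day window also assumes that cystectomy is not itself treated as new anticancer therapy, which would shorten the window to 30 days after stopping; nothing in the protocol says that it is. The number of patients and of missed events cannot be estimated from the documents. The effect on a decision is confined to counts near a boundary. This should be corrected because it touches the main safety endpoint and costs little.

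**What to change.** **5.8 and 7.14.** Separate stopping the drug from leaving the trial. Every patient who received at least one dose and has cystectomy completes the existing 30- and 90-day post-operative visits in addition to the discontinuation visit, unless consent is withdrawn. State that this includes a patient whose withheld second dose is never given.

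**9.4.** Carry the all-treated-patients set of 2.1.7 into the TOX denominator. If any 30-day post-operative status is unknown, report the TOX rate and interval twice, with those patients counted as no TOX and as TOX.

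**Cost.** A short amendment, and two already defined visits for each early stopper who has surgery. N, the prior and the stopping boundaries stay as they are.
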